### **Change from baseline in BPDAI activity score at Week 36**

BPDAI activity score is a continuous endpoint that will be completed at the visits specified in the SoA ([Table 2](#)) during the initial 36-week treatment period.

The estimand strategy is outlined in [Table 10](#) above. For this endpoint, intercurrent events of rescue use with OCS after having previously achieved disease control and restricted medication use are considered unfavorable outcomes and will be handled with a composite strategy whereby participants experiencing these events prior to Week 36 will have their last observation prior to rescue/restricted medication use carried forward to Week 36. For participants who discontinue the study without having rescue or restricted medications, missing data at Week 36 will be imputed using multiple imputation based on participants who don't have rescue/restricted medication use. Once these imputations are made, the available change from baseline in BPDAI score at Week 36 will then be analyzed using an analysis of covariance (ANCOVA) model.

The model will include change from baseline at Week 36 as the dependent variable, baseline BPDAI score as a continuous covariate, and treatment, baseline disease severity, and time of

BP diagnosis as categorical covariates. The model will be used to estimate the mean change from baseline at Week 36 for each treatment group and the difference versus placebo, with corresponding 95% confidence limits. A p-value, corresponding to a 2-sided test, will be presented to compare the benralizumab and placebo treatment groups.

To support this analysis, observed means and mean changes from baseline will be summarized using descriptive statistics by treatment group and each scheduled visit up to Week 36. In addition, the cumulative distribution function of absolute changes from baseline in BPDAI activity score at Week 36 will also be plotted, to allow the treatment difference at various response thresholds to be explored. Responder analyses using minimal clinically important differences presented in the literature ([Wijayanti et al 2017](#)) may be presented, if appropriate.

### **Change from baseline in BPDAI-Pruritus score at Week 36**

BPDAI-Pruritus score is a continuous endpoint that will be completed at the visits specified in the SoA ([Table 2](#)) during the initial 36-week treatment period. The statistical analysis described above for BPDAI activity score will be carried out for this endpoint, with the same estimand approach and the same ANCOVA model will be fitted to these data.

To support this analysis, observed means and mean changes from baseline will be summarized using descriptive statistics by treatment group and each scheduled visit up to Week 36. In addition, the cumulative distribution function of absolute changes from baseline in BPDAI-Pruritus score at Week 36 will also be plotted to allow the treatment difference at various response thresholds to be explored.

#### **9.4.2.3 Analysis Methods for Secondary Efficacy Variables**

##### **Proportion of participants in sustained complete/partial remission on minimal OCS/off OCS for at least 2 months at Week 36**

A supportive responder analysis will be performed where any participant who achieved complete or partial remission, while on minimal OCS or off OCS for at least 2 months at Week 36 will be defined as responders. The statistical methodology described for the primary analysis will be carried out for this endpoint.

Summaries of the different combinations of complete and partial remission, each on minimal OCS or off OCS, will also be produced to understand the distribution of these clinical benefit categories at visits throughout the study up to Week 36.

##### **Cumulative time (weeks) in complete remission off OCS from baseline to Week 36**

Cumulative time in complete remission while off OCS will be derived for each participant over the initial 36-week treatment period. These times will then be assigned to a set of ordered categories (which will include a category for no weeks in complete remission off OCS), to be

fully defined in the SAP. An ordered logistics regression model will be fitted to these categories, assuming proportional odds.

The model will include cumulative time as the dependent variable and treatment, baseline disease severity and time of BP diagnosis as categorical covariates. The model will be used to estimate an odds ratio, with 95% CIs.

### **Proportion of participants off OCS by Week 36**

Participants will be defined as responders if they are off OCS by Week 36. Otherwise, participants will be classified as non-responders. The statistical methodology described for the primary analysis will be carried out for this endpoint. (The p-value will be nominal, as secondary objectives are not controlled for multiplicity and do not appear in the testing hierarchy.) To support this analysis, the observed proportion of responders will be summarized using descriptive statistics by treatment group and each scheduled visit up to Week 36.

### **IGA score at Week 36 and change from baseline in IGA score at Week 36**

IGA score achieved (clear, almost clear, mild, moderate, severe) will be summarized using descriptive statistics by treatment group at each scheduled visit up to Week 36.

A responder analysis will be performed where participants will be classified as responders if they achieve IGA 0/1 (ie, clear or almost clear) at Week 36. Otherwise, participants will be classified as non-responders. The statistical methodology described for the primary analysis will be carried out for this endpoint (the p-value will be nominal, as secondary objectives are not controlled for multiplicity and do not appear in the testing hierarchy).

Number of points change from baseline in IGA score will be summarized, and a shift table comparing IGA score at baseline against IGA score achieved at Week 36 (and other visits throughout the study, as relevant) will be produced.

### **Proportion of participants who remain relapse-free up to Week 16**

Referring to the statistical analysis for the proportion of participants who remain relapse-free up to Week 36, proportion of participants who remain relapse-free up to Week 16 will also be analyzed as a binary endpoint with a similar logistic regression model.

### **Proportion of participants with any clinical benefit at Week 16**

To assess signs of clinical efficacy during the first 16 weeks of the study, the observed proportion of participants showing partial remission or complete remission at Week 16 will be summarized using descriptive statistics by treatment group. The summary will categorize each of these disease states into: during taper, with no steroids, and with minimal steroids (ie, < 0.1 mg/kg/day).

If a consistent message can be drawn across these categories and treatment groups, a supportive analysis will be carried out, whereby a participant will be classified as a responder if they show any clinical benefit (ie, partial remission or complete remission) during taper, with no steroids or with minimal steroid use at Week 16. Otherwise, a participant will be classified as a non-responder. This binary variable will then be analyzed using a logistic regression model with a logit link function. The model will include treatment, baseline disease severity and time of BP diagnosis as covariates. The model will be used to estimate the proportion of responders for benralizumab and placebo, the difference between these proportions (benralizumab – placebo) and an odds ratio, with corresponding 95% confidence limits. A p-value, corresponding to a 2-sided test, will be presented to compare the benralizumab and placebo treatment groups. (The p-value will be nominal, as secondary objectives are not controlled for multiplicity and do not appear in the testing hierarchy.)

#### **Time to disease control, OCS dose at disease control and time to the end of the consolidation phase**

Time to disease control, OCS dose at disease control and time to the end of the consolidation phase will be summarized using descriptive statistics by treatment group. The time to disease control and time to the end of the consolidation phase may also be grouped into ordered categories and summarized by treatment group. Statistical analysis and Kaplan Meier plots may be performed if appropriate. Full details will be provided in the SAP.

#### **Change from baseline in BPDAI activity score at Week 16**

Referring to the statistical analysis for change from baseline in BPDAI activity score at Week 36, the same analysis methods will be used for the change from baseline at Week 16 endpoint (the p-value at Week 16 will be nominal, as secondary objectives are not controlled for multiplicity and do not appear in the testing hierarchy).

#### **Change from baseline in BPDAI-Pruritus score at Week 16**

Referring to the statistical analysis for change from baseline in BPDAI-Pruritus score at Week 36, the same analysis methods will be used for the change from baseline at Week 16 endpoint (the p-value at Week 16 will be nominal, as secondary objectives are not controlled for multiplicity and do not appear in the testing hierarchy).

#### **9.4.3 Safety Analyses**

Summaries will be based primarily on the safety analysis set and focus on the initial 36-week treatment period. A key subset of these summaries will also be repeated for the entire study period and the OLE. Full details will be provided in the SAP.

#### **9.4.3.1 Adverse Events**

Adverse events will be coded using the most recent version of the Medical Dictionary for Regulatory Activities (MedDRA) that will have been released for execution at AstraZeneca/designee.

Safety data will be presented using descriptive statistics, unless otherwise specified.

Adverse events will be presented for each treatment group by system organ class and preferred term, including the number and percentage of participants reporting at least 1 event, number of events and exposure-adjusted rates, where appropriate.

An overview of AEs will be presented for each treatment group, including the number and percentage of participants with any AE, AEs with outcome of death, serious AEs, and AEs leading to discontinuation of IP.

Separate AE tables will be provided taking into consideration the relationship as to IP assessed by the Investigator, maximum intensity, seriousness, death and events leading to discontinuation of IP, as well as other action taken related to IP.

An additional table will present number and percentage of participants with most common AEs (frequency of  $\geq 3\%$ ).

In accordance with the requirements of the Food and Drug Administration, a separate table will present non-serious AEs occurring in more than 5% of participants in any treatment group.

Key participant information will be presented for participants with AEs with outcome of death, serious AEs, and AEs leading to discontinuation of IP.

An AE listing for the safety analysis set will cover details for each individual AE.

#### **9.4.3.2 Treatment Emergence**

The following events are considered treatment emergent:

- AEs with an onset date on or after the first dose of IP
- Worsening of pre-existing events on or after first dose of IP

#### **9.4.3.3 Clinical Safety Laboratory Assessments**

Laboratory data for hematology and clinical chemistry will be summarized. The frequency of changes with respect to normal ranges between baseline and each post-treatment time point will be tabulated. Frequencies of clinically noteworthy values (defined in the SAP) occurring during the clinical study will also be given.

#### **9.4.3.4 Vital Signs**

Details of all vital signs analyses will be provided in the SAP. As an overview, descriptive statistics will be presented for observed and change from baseline values for all vital sign parameters, which include the continuous measures: systolic blood pressure, diastolic blood pressure, pulse rate, respiration rate and body temperature.

For each treatment group:

- The parameters will be summarized at each scheduled post-baseline visit and will include: number of available observations, mean, standard deviation, median, minimum and maximum, and quartiles where more appropriate.
- The number and percentage of participants falling into specific vital signs categories (defined in the SAP) will be presented at each scheduled post-baseline visit in a frequency table.
- Changes in vital signs measurements will be examined at each scheduled post-baseline visit and clinically noteworthy values observed during the study (defined in the SAP) will be presented in a frequency table.

#### **9.4.3.5 Body Weight**

For each treatment group, descriptive statistics will be presented for observed and change from baseline values at each scheduled post-baseline visit and will include: n, mean, standard deviation, minimum, Q1, median, Q3 and maximum. Changes in body weight will be examined at each scheduled post-baseline visit and clinically noteworthy values observed during the study (defined in the SAP) will be presented in a frequency table.

### **9.4.4 Pharmacokinetic Analyses**

The PK analyses will be performed at or under the guidance of AstraZeneca Research and Development. Benralizumab serum concentrations will be summarized using descriptive statistics at each scheduled visit for participants in the PK analysis set.

### **9.4.5 Immunogenicity Analyses**

Anti-drug antibodies to benralizumab will be summarized using descriptive statistics by treatment group and each visit specified in the SoA ([Table 2](#)). The ADA titers-time profiles of benralizumab may be generated. The impact of ADA on PK and eosinophil level will be assessed. The potential association of ADA with safety and efficacy will be evaluated. Full details will be provided in the SAP.

CC1

#### **9.4.6.1 Patient-reported Outcomes**

Quality of life will be assessed using the AB-QoL total score and the EQ-5D-5L score at the visits specified in the SoA ([Table 2](#)). For each of these continuous endpoints, observed means and mean changes from baseline will be summarized using descriptive statistics by treatment group and each scheduled visit. To support these summaries, an MMRM model may be fitted to each of these outcome variables if deemed appropriate, following the details outlined in Section [9.4.2.2](#) for BPDAI activity score.

Itch will be assessed using the Peak Pruritus NRS and recorded every day from Visit 2 onwards by participants using a handheld device. Note that this endpoint is not collected during the screening period and so a baseline score will not be available. All changes will be assessed in an exploratory manner, relative to disease control. Analyses of the Peak Pruritus NRS endpoint will be completed in the subset of patients able to use the handheld device.

For each participant, if at least 4 non-missing daily assessments are available in a weekly period, a weekly mean score will be derived starting from the seventh day after disease control, by summing the daily score over the available assessment and dividing by the number of available assessments in that week. If there are less than 4 non-missing daily assessments included in the calculation of the weekly score, the weekly score is missing for that week. The weekly scores will be summarized by descriptive statistics for observed means and mean changes from disease control.

Binary endpoints will be derived using these weekly mean scores, whereby participants will be classified as a responder or a non-responder for each week using pre-specified clinically meaningful thresholds. As no threshold for a clinically relevant within-person response definition has been established for BP, the  $\geq$  2- to 4-point change threshold proposed for atopic dermatitis by [Yosipovitch et al 2019](#) will be used for this study. Atopic dermatitis is an appropriate comparison point as it is another intensely pruritic inflammatory skin condition associated with eosinophilia ([Jenerowicz et al 2007](#)). Therefore, in the current study, a participant will be considered to have an improvement for a given week if a  $\geq$  2-point reduction versus disease control is observed and will be considered to have a worsening for a given week if a  $\geq$  2-point increase versus disease control is observed for the weekly mean score. However, depending on distribution of the data, other thresholds for response may be explored. The responder definition will be finalized and documented before unblinding.

Observed proportion of responders will be summarized using descriptive statistics by treatment group and week.

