**Table 3** **Schedule of PRO Assessments**

Instruments	Schedule
Peak Pruritus Numeric Rating Scale and OCS Usage	First assessment at site at V2, then at home every evening (17:00-23:59) starting the day after V2 at home thereafter until V22 (Week 72). a
BPDAI-Pruritus, AB-QoL, EQ-5D-5L	At site at every visit up to V22 (Week 72), and then every 12 weeks thereafter. At site at unscheduled, IPD, and follow-up visits.

a Participants will complete BPDAI-pruritus, AB-QoL, and EQ-5D-5L onsite using the tablet. Some participants may be exempted from completing the at home PRO assessments on the handheld device (ie, Peak Pruritus Numeric Rating Scale and OCS Usage) upon agreement with the AstraZeneca physician.  
AB-QoL, Autoimmune Bullous Disease Quality of Life; BPDAI, bullous pemphigoid disease area index; EQ-5D-5L, European Quality of Life-5 Dimensions; IPD, investigational product discontinuation; OCS, oral corticosteroids; PRO, patient-reported outcomes; V, visit.

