#### 4.1.2 Double-blind Treatment Period

Approximately 120 eligible participants will be randomized 1:1 at baseline (Visit 2), to receive either benralizumab or placebo every 4 weeks (Q4W) by subcutaneous (SC) injection.

The randomization will be stratified by disease severity and time of BP diagnosis (participants with newly diagnosed BP; participants with a previous diagnosis of BP who have relapsed). Bullous pemphigoid disease area index (BPDAI) activity score will be used to assess disease severity, whereby participants with a score greater than or equal to 56 points will be classified as severe. The double-blind treatment period for each participant will last for 36 weeks.

Participants will receive a loading dose of either 60 mg benralizumab or placebo, administered as 2 SC injections at Visit 2. After 4 weeks, participants will receive 30 mg benralizumab or placebo Q4W per their initial randomization until the end of the double-blind treatment period. Starting at Visit 2, participants will also receive OCS 0.5 mg/kg/day until BP disease control is achieved. In participants who do not achieve disease control, the OCS dose can be increased (eg, 0.75 mg/kg; [\(Feliciani et al 2015\)](#) to achieve disease control. The steroid doses and time necessary to achieve disease control of BP may vary between participants.

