## **Before IP Administration**

All applicable visit procedures, including collection of biomarker, PK, and ADA samples and on-site PRO assessments, should be completed prior to IP administration.

[figure not shown]
Prior to each IP administration:

- Investigator, or designee, will evaluate the participant's condition for potential contraindications for dosing (Section [6.1.2](#)).
- Investigator, or designee, will assess the injection site as per standards of medical care.

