### **8.1.2 Patient-reported Outcomes**

Participants will complete all PRO assessments using provisioned devices. All participants will complete PROs on the tablet at onsite visits. Daily PROs are completed on the handheld device at home. If the Investigator believes that the participant has a medical condition (eg, BP skin lesions on the fingers/hand, neurologic condition affecting the fingers/hand, or severe visual impairment), then an exemption from at-home PROs may be requested from the AstraZeneca study physician prior to the screening visit.

The Investigator will ensure that participants are properly trained on the use of the handheld PRO device and the importance of completing at-home assessments as scheduled. Compliance should be checked weekly (at a minimum) to ensure that the participant is completing the assessments as scheduled, including a check of the daily oral steroid doses taken. The Investigator or designee will be responsible for monitoring participant adherence with the daily assessments and follow up as necessary.

The at-home handheld device will be programmed at Visit 2 with reminder alarms for the daily questionnaires. Study site staff will be able to adjust alarms for specific participant needs as needed. The participant will be required to complete a training module before taking the device home.

Participants must bring the at-home handheld device to every visit.

Confirmation of the visit in the PRO system, completion of at-site PRO assessments, and review of participant compliance with at-home PRO assessments should be completed prior to other study procedures. The timing and frequency for each PRO is provided in [Table 3](#). The handheld device will be returned to the study site at Visit 22 (Week 72) or at the IPD visit for participants who prematurely discontinue from IP and are unwilling/unable to continue with visit procedures.

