3.6 Tertiary/exploratory outcome variables

3.6.1 Peak Pruritus Numeric Rating Scale

The Peak Pruritus NRS is a one-item assessment that asks participants to rate the intensity of their worst itch during the past 24 hours. The scale ranges from 0 (no itch) to 10 (worst itch imaginable).

Participants will be asked to record their Peak Pruritus NRS assessment using a handheld device at site at Visit 2, then at home every evening starting the day after Visit 2 thereafter

until Week 72 (Visit 22). Note that this endpoint is not collected during the screening period and so a baseline score will not be available. All changes will be assessed in an exploratory manner, relative to disease control.

Weekly mean scores will be computed for each week starting from the 7th day after disease control. Change will be assessed by comparison to the assessments on the date when disease control was recorded and on the 6 days after as per Section [3.1.1](#).

For each participant, weekly mean scores will be calculated by summing the daily score over the past 7 days. If a daily assessment is missing, the corresponding daily score is missing. If a participant has at least 4 non-missing daily assessments included in the calculation of the weekly score, the weekly mean score is defined as the sum of the available daily assessments in that week, divided by the number of days with non-missing daily assessments. If there are less than 4 non-missing daily assessments included in the calculation of the weekly score, then the weekly mean score is missing for that week.

Binary endpoints will be derived using weekly mean scores, whereby participants will be classified as a responder or a non-responder for each week using pre-specified clinically meaningful thresholds.

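### Peak Pruritus change is measured only from disease control because no baseline is said to exist, although a single-day score is scheduled at Visit 2

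*Protocol*

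**What the plan says.** Protocol 9.4.6.1 gives the reason and the consequence in consecutive sentences: "Note that this endpoint is not collected during the screening period and so a baseline score will not be available", and then "All changes will be assessed in an exploratory manner, relative to disease control". SAP 3.6.1 carries both statements. SAP 3.1.1 defines the reference as the scores on the day disease control is recorded and the six days after it.

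Weekly means need at least 4 daily scores and are derived from the seventh day after disease control. A participant improves in a given week if the weekly mean is at least 2 points below the disease-control reference.

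The schedule reads differently. Protocol Table 3 has "First assessment at site at V2, then at home every evening (17:00-23:59) starting the day after V2". SAP 3.6.1 agrees: "Participants will be asked to record their Peak Pruritus NRS assessment using a handheld device at site at Visit 2". Protocol 4.1.2 calls Visit 2 baseline and randomizes there. Two further rules bear on the order of events at that visit:
- The part of Protocol 6.1.1 on steps before dosing says "on-site PRO assessments, should be completed prior to IP administration".
- Protocol 8.1.2 says "completion of at-site PRO assessments, and review of participant compliance with at-home PRO assessments should be completed prior to other study procedures".

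**The concern.** That a score is not taken during screening does not mean that no baseline score exists. One is planned at the randomization visit, and the stated ground for dropping a pre-treatment reference therefore fails as written.

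The replacement reference can be affected by treatment. Disease control comes after randomization. Protocol Table 6 defines it partly by pruritus starting to abate, and time to disease control is itself a secondary endpoint, so the plan allows for it to differ by arm. SAP 4.2.6.2 recognises the same difficulty elsewhere: it reports the subgroups by OCS dose at disease control separately because that dose is not a baseline variable.

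At stake is whether the daily itch data describe the treatment comparison from randomization onward, or only what happens after each participant has reached control.

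**Working it through.** There is no stated figure to reproduce. The check sets the sections side by side and then works through the arithmetic of the reference point.

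**Is there a baseline score?**
1. Table 3 and SAP 3.6.1 place the first NRS on site at Visit 2.
2. Protocol 6.1.1 and 8.1.2 put on-site patient-reported outcomes before dosing and before other procedures. Pre-dose timing of the NRS follows from combining these with Table 3; no sentence states it for this score.
3. The general efficacy rule in SAP 3.1.1 takes the last value on or before the date of randomization, and treats same-day values without a time as earlier than randomization. A Visit 2 score fits that rule, but the same section then gives the NRS its own reference.
4. One daily score cannot meet the 4-of-7 rule. A weekly-mean baseline is unavailable; a single-day baseline score is not.

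**What does the disease-control reference remove?** Suppose the arms have equal means at Visit 2. Let *D* be the between-arm difference (benralizumab minus placebo) at disease control. Then:

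difference in change from control = difference in change from Visit 2 − *D*

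All scores below are assumed.

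| Case | Visit 2, both arms | Control, benralizumab / placebo | Week 36, benralizumab / placebo | Difference from Visit 2 | *D* | Difference from control |
|---|---|---|---|---|---|---|
| A | 7 | 3 / 5 | 1 / 3 | (1−7) − (3−7) = −2 | −2 | (1−3) − (3−5) = 0 |
| B | 7 | 5 / 5 | 2 / 4 | (2−7) − (4−7) = −2 | 0 | (2−5) − (4−5) = −2 |
| C | 8 | 4 / 6 | 3 / 4 | (3−8) − (4−8) = −1 | −2 | (3−4) − (4−6) = +1 |

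In A the difference vanishes, in B nothing is lost, and in C the sign reverses. If *D* were positive, change from control would flatter benralizumab. The loss is exactly *D*, and the documents give no means from which to estimate it.

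**Other consequences of the rule**
- A participant who never reaches control has no reference for change.
- A participant whose control-week mean is below 2 cannot fall by 2 points, because the scale stops at 0.
- Daily scores before control never enter the planned weekly summaries.

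**How noisy is one day?** With between-participant SD *b* and day-to-day SD *w*, the reliability of a *k*-day mean is *b*² / (*b*² + *w*²/*k*). The documents give neither SD, so these ranges assume *b* from 1.5 to 2.5 and *w* from 1 to 2:
- single score: 2.25/(2.25 + 4) = 0.36 up to 6.25/(6.25 + 1) = 0.86
- 7-day mean: 2.25/(2.25 + 4/7) = 0.80 up to 6.25/(6.25 + 1/7) = 0.98

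**The case against.** The strongest reply is that the endpoint is a weekly mean. In context, the sentence may mean only that this endpoint's own baseline cannot be formed, and SAP 3.1.1 makes an explicit exception for the NRS. Placing one day's score inside a 2-point rule compares a noisy value with a 7-day mean, in participants enrolled with active disease, and so invites regression to the mean. This stands as a limit on how the Visit 2 score may be used. It does not rescue the statement that no baseline score will be available, nor does it make a post-randomization reference neutral.

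Pre-dose timing is also an inference. The Table 3 footnote lists the on-site tablet instruments without the NRS and classes the NRS among the at-home assessments. That stands too, although the same table puts the first NRS on site.

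The stakes are limited. The endpoint is tertiary, summarized descriptively and outside the testing hierarchy. SAP 3.6.1 allows a response definition based on an absolute score and counts otherwise missing data as non-response, which plausibly covers participants who never reach control in the binary summary. Few may be affected: Protocol 2.2.1 cites a study with 91% disease control at 3 weeks on oral corticosteroids.

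Two stronger readings are tempting, and the documents support neither:
- A reader might infer that early itch benefit is lost to the trial. BPDAI-Pruritus is collected from screening, includes a 24-hour item, and is analysed as change from baseline at Week 16 and, as a key secondary endpoint, at Week 36.
- A reader might infer from case C that the plan will favour the wrong arm. That needs a gap at control that later narrows, and nothing in the documents shows one.

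**Conclusion.** The point holds as an inconsistency with a practical consequence for an exploratory endpoint. A single-day score is scheduled at the randomization visit, and only a weekly-mean baseline is unavailable. With disease control as the sole reference, any between-arm itch difference already present at control is subtracted, participants without control drop out of the change summaries, and the weeks before control go unreported. The distortion equals the between-arm difference at control: zero if the arms are alike there, and otherwise of unknown size and direction.

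This rests on three assumptions: the Visit 2 score is completed before dosing, as the visit-order rules imply; the arms are comparable at Visit 2 through randomization; and the analysis is confined to participants who use the handheld device. It would not justify simply substituting the Visit 2 score into the responder rule without dealing with its one-day limitation.

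**What to change.** 1. Correct the sentence in Protocol 9.4.6.1 and SAP 3.6.1: a single-day score exists at Visit 2, and no weekly-mean baseline does. State that the Visit 2 NRS is to be completed before dosing.
2. Derive weekly means from randomization for all handheld users, under the existing 4-of-7 rule, and report them by arm.
3. Report change from the Visit 2 score, or weekly means adjusted for it, with responder status on that basis and the one-day limitation stated. The responder definition is still to be finalized before unblinding, so the plan leaves room for this.
4. Keep change from disease control as a supplementary description, and give the number in each arm with no reference value. Align SAP 3.1.1.

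The cost is wording and some extra tables; no new data are needed. The downside is a noisier baseline that is subject to regression to the mean. Because the score is taken at randomization, this should apply equally to both arms: it lowers precision and can shift the absolute responder rates, but should not bias the comparison between arms.
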